## 2. STUDY DESIGN

This single-arm, multicenter, open label Phase IIIb clinical study will enroll patients aged 12 years or older with congenital hemophilia A who have persistent inhibitors against FVIII at enrollment. Approximately 200 patients with inhibitors will be enrolled globally. Patients will receive prophylactic emicizumab at 3 mg/kg/week subcutaneously for 4 weeks, followed by 1.5 mg/kg/week subcutaneously for the remainder of the 2-year treatment period (Figure 1).

**Figure 1 – Study Design**

The primary objective of this study is to evaluate the overall safety and tolerability of prophylactic administration of emicizumab in patients with congenital hemophilia A who have persistent inhibitors against FVIII at enrollment. In order to achieve this objective, all adverse events, including adverse events of special interest, will be captured on an ongoing basis, as they occur during the study. Physical examinations, vital signs, and laboratory values will be assessed as per the Schedule of Activities (Appendix 2: Schedule of Activities).

The secondary objective of this study is to evaluate the efficacy of prophylactic administration of emicizumab. As part of this objective, the number of bleeds over time will be recorded for all of the enrolled patients.

The final analysis will be conducted when all patients have completed 2 years of treatment or have withdrawn, whichever occurs sooner. Patients, or their legally authorized representative, will be asked to report bleed information on an electronic patient-reported outcome (ePRO) device where possible, including site of bleed, type of bleed, time of each individual bleed (day, start and stop time), and treatment for bleed. HRQoL will be assessed and the EuroQoL Five-Dimension-Five Levels Questionnaire (EQ-5D-5L) will be completed prior to the first emicizumab administration (Week 1), at the Month 3, 6, 12, and 18 assessments, and at study completion as outlined in the Schedule of Activities (Appendix 2: Schedule of Activities). Additional secondary endpoints include assessing patient preference for the emicizumab regimen compared with the previous regimen using a questionnaire (EmiPref).

## **2.1                    PROTOCOL SYNOPSIS**

The Protocol Synopsis is in Appendix 1. For additional details, see the Schedule of Assessments in Appendix 2: Schedule of Activities.

## 2.2 OBJECTIVES AND ENDPOINTS

- To evaluate the overall safety and tolerability of prophylactic administration of emicizumab (primary objective): Incidence and severity of all adverse events (AEs), including AEs of special interest, AEs leading to discontinuation and SAEs will be analyzed. Additionally, changes in physical examination findings, vital signs and laboratory parameters will be presented.
- To evaluate the efficacy of prophylactic administration of emicizumab (secondary objective): the number of bleeds over time, the HRQoL of patients according to Haem-A-QoL ( $\geq 18$  y) or Haemo-QoL-SF (ages 12–17) scores, the health status of patients according to EQ-5D-5L scores over time and the patient preference for the emicizumab regimen compared with the previous regimen used are shown.
- To evaluate the immunogenicity of emicizumab (immunogenicity objective): the occurrence and clinical significance of anti-emicizumab antibodies are assessed.
- Emicizumab PK data (pharmacokinetic objective) at defined time points are analyzed.

### 2.2.1 Adverse Events of Special Interest

Adverse events of special interest (AESI) for this study include the following:

- Cases of potential drug-induced liver injury that include an elevated ALT or AST in combination with either an elevated bilirubin or clinical jaundice, as defined by Hy's law (see Protocol Section 5.3.5.7).
- Suspected transmission of an infectious agent by the study drug, as defined below. Any organism, virus, or infectious particle (e.g., prion protein transmitting transmissible spongiform encephalopathy), pathogenic or non-pathogenic, is considered an infectious agent. A transmission of an infectious agent may be suspected from clinical symptoms or laboratory findings that indicate an infection in a patient exposed to a medicinal product. This term applies only when a contamination of the study drug is suspected.
- Systemic hypersensitivity reactions and anaphylactic and anaphylactoid reactions (see Sampson's Criteria in Protocol Appendix 4).
- Thromboembolic events.
- Microangiopathic hemolytic anemia or TMA (e.g. hemolytic uremic syndrome).

### 2.2.2 Bleed Assessments

Patients will be trained on how to record their bleeds and hemophilia medication use using an ePRO device. When bleeds occur, patients will need to record the site of bleed, type of bleed, time of each individual bleed (day, start and stop time), and treatment for bleed. At least once a week, patients will need to record any hemophilia medication use (including emicizumab) and information regarding any bleeding events. Investigator review of patient-reported bleed/medication records with the patient/caregiver will occur for completeness and accuracy throughout the study.

### **2.2.2.1 Definition of a Bleed**

For the purposes of the efficacy analyses, a standardized definition of bleed, adapted from the standard criteria defined by the FVIII and FIX Subcommittee of the Scientific and Standardization Committee (SSC) of the International Society on Thrombosis and Haemostasis (ISTH), that is similar to the definition used in a recent clinical investigation, will be utilized in this study (Blanchette et al. 2014; Mahlangu et al. 2014):

An event is considered a bleed if coagulation factors are administered to treat signs or symptoms of bleeding (pain, swelling, etc.). An additional definition of all reported bleeds (irrespective of treatment with coagulation factors) will be applied for a separate analysis.

### **2.2.2.2 Treated bleeds**

A bleed is considered to be a “treated bleed” if it is directly followed (i.e., there is not an intervening bleed) by a hemophilia medication reported to be a “Treatment for bleed” (see Haemophilia Medication Record) irrespective of the time between the treatment and the preceding bleed. Note, a bleed occurring at the same time as a treatment, counts as a treated bleed. A bleed and the first treatment thereafter are considered to be pairs (i.e., one treatment belongs to one bleed only), with the following exception: if multiple bleeds occur on the same calendar day, the subsequent treatment is considered to apply for each of these multiple bleeds.

Bleeds due to surgery/procedure will not be included in the primary analysis. In addition, treatments reported as “Treatment for bleed” directly following a bleed due to surgery/procedure are excluded.

### **2.2.2.3 72-Hour rule**

Two bleeds of the same type (e.g., “joint,” “muscle,” or “other”) and the same etiology and at the same anatomical location are considered to be one bleed if the second occurs within 72 hours from the last treatment for the first bleed. Any bleed with a different etiology is considered a separate bleed regardless of time from last injection. The last treatment is defined as the last treatment before a new bleed occurs, either in the same or in a different location. This is in-line with the above definition that bleeds and treatments are considered to be pairs.

If the bleed location is other/other, other/other is used as the bleed location and not the exact location entered on the separate eCRF page.

In case of trauma with multiple different locations of bleed, this will be considered as one bleed for the analyses. However, all data will be collected, including the various locations of the different bleeds.

A listing of all bleeds is produced. The listing includes all bleed and hemophilia medication, except emicizumab, information entered on the Bleed Record, with an indicator which bleeds are included in the primary analysis and which do not count as separate bleeds due to the 72h rule.

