##### **4.5.7.1 Definition of a Bleed**

For the purposes of the efficacy analyses, a standardized definition of bleed, adapted from the standard criteria defined by the FVIII and FIX Subcommittee of the Scientific and Standardization Committee (SSC) of the International Society on Thrombosis and Haemostasis (ISTH), that is similar to the definition used in a recent clinical investigation, will be utilized in this study ([Blanchette et al. 2014](#); [Mahlangu et al. 2014](#)):

- An event is considered a bleed if coagulation factors are administered to treat signs or symptoms of bleeding (pain, swelling, etc.). An additional definition of all reported bleeds (irrespective of treatment with coagulation factors) will be applied for a separate analysis.
- Bleeds starting from the first sign of a bleed and ending 72 hours after the last treatment for the bleed, which have any symptoms of bleeding at the same location or injections are  $\leq 72$  hours apart, are considered the same bleed.
- Any injection to treat the bleed, taken  $> 72$  hours after the preceding injection, is considered the first injection to treat a new bleed at the same location.
- In case of trauma with multiple different locations of bleed, this will be considered as one bleed for the analyses. However, all data will be collected, including the various locations of the different bleeds.
- Any bleed with a different etiology is considered a separate bleed regardless of time from last injection.

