#### **4.6.1.6 Use of non-emicizumab hemophilia treatments**

The number of treatments to treat a bleed will be summarized. The number of infusions is counted per bleed corresponding to the definition of the primary endpoint, i.e. all treatments that are linked to the same bleed per the 72h rule are considered to belong to the same bleed. If the same treatment/s are associated with multiple bleeds, these are counted multiple times, i.e. linked to both bleeds.

The cumulative dose per kg administered will be summarized by product, e.g. RECOMBINANT FACTOR VIIA [E.G. NOVOSEVEN] or PROTHROMBIN COMPLEX CONCENTRATE [E.G. FEIBA]. The following formulas will be used to annualize the dose and the number of infusions:

$$\frac{\text{Number of Infusions}}{\text{Efficacy Period}} \times 365.25$$

$$\frac{\text{Cumulative dose/kg}}{\text{Efficacy Period}} \times 365.25$$

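### The SAP omits the protocol rule that an injection more than 72 hours after the previous one opens a new bleed; where such gaps occur without a new bleed record, treated bleeds are undercounted

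*SAP*

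**What the plan says.** Protocol 4.5.7.1 defines a bleed for the efficacy analyses and uses 72 hours in two separate rules. One merges: "Bleeds starting from the first sign of a bleed and ending 72 hours after the last treatment for the bleed", with symptoms at the same site or injections no more than 72 hours apart, count as the same bleed. The other splits: an injection taken more than 72 "hours after the preceding injection, is considered the first injection to treat a new bleed at the same location". The splitting rule needs no new symptom report.

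SAP 2.2.2.1 to 2.2.2.4 carries over the treated-bleed idea, the etiology rule, the multi-site trauma rule and a merging rule. Two recorded bleeds of the same type, etiology and site "are considered to be one bleed if the second occurs within 72 hours from the last treatment for the first bleed". The end point of the earlier bleed is fixed by this sentence: "The last treatment is defined as the last treatment before a new bleed occurs, either in the same or in a different location". Treatments are tied to bleeds by order in time: "A bleed and the first treatment thereafter are considered to be pairs", and a bleed counts as treated "irrespective of the time between the treatment and the preceding bleed". No sentence limits the gap between successive treatments of one bleed, and none opens a bleed from an injection.

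SAP 4.6.1.6 and 4.9.1.2 use the same unit for infusions, dose per kg and treatment duration per bleed: "all treatments that are linked to the same bleed per the 72h rule are considered to belong to the same bleed".

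**The concern.** Treated bleeds are the event on which SAP 4.6.1.1 bases its main efficacy analysis. If a patient injects for a bleed, waits more than 72 hours and injects again without logging a new bleed, the protocol counts two bleeds and the SAP counts one. The later injection also moves the 72-hour window forward, so a subsequent recorded bleed at that site can be absorbed as well. Someone following the SAP exactly would then report a count that conflicts with the protocol's definition, and no SAP section states or justifies the difference.

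The sensitivity analyses in SAP 4.6.6 do not help. The one that drops the 72-hour rule still counts recorded bleeds, so it cannot recover a bleed that exists only because of an injection gap. The other two restrict the patients or the follow-up time.

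The per-bleed exposure summaries are exposed too. Two courses more than 72 hours apart can be reported as one course with the summed dose and the full elapsed time, including for activated prothrombin complex concentrate.

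**Working it through.** **Inputs.** The merging and splitting rules in Protocol 4.5.7.1; the pairing, 72-hour and all-bleeds rules in SAP 2.2.2.2 to 2.2.2.4; the six worked examples in SAP 2.2.2.4; the ABR formula in SAP 4.6.1.1. RE and LE are recorded right and left elbow bleeds; T is a treatment for bleed.

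**Step 1: reproduce the SAP's own counts.** Assign each T to the most recent recorded bleed. Start the 72 h at the last T before the next recorded bleed, or at the bleed itself if untreated. Merge a same-site bleed that starts within 72 h of that point.

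1. RE–2h–T–75h–RE–2h–T: 75 > 72, so 2.
2. RE–75h–RE–2h–T: 75 > 72, so 2.
3. RE–70h–RE–2h–T: 70 ≤ 72, so 1.
4. RE–50h–RE–30h–RE: both gaps ≤ 72, so 1.
5. RE–30h–RE–25h–LE: the two RE merge and LE is separate, so 2.
6. The long example: the second RE merges (35 h) and the second LE merges (45 h). The last RE comes 2 + 45 + 70 = 117 h after the previous RE record, so 3.

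All six match the SAP (2, 2, 1, 1, 2, 3).

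**Step 2: add only the protocol's splitting rule and recount treated bleeds.**

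| Sequence | SAP | With protocol rule |
|---|---|---|
| RE–2h–T–100h–T–60h–RE | 1 | 2 |
| RE–2h–T–75h–T | 1 | 2 |
| RE–2h–T–100h–T–100h–T | 1 | 3 |
| RE–2h–T, then four more T at 24 h intervals | 1 | 1 |
| RE–2h–T–75h–RE–2h–T (second bleed recorded) | 2 | 2 |

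In the first row the 100 h gap opens bleed 2, and the last RE falls 60 h after the second T, so it belongs to bleed 2. Under the SAP the window runs from the second T, 60 ≤ 72, and everything is one bleed. The six SAP examples do not change, because none has an injection gap above 72 h without a new record.

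**Step 3: direction of this omission.** Let G be the number of gaps above 72 h between successive treatments assigned to one recorded bleed. The rule adds one bleed per gap and moves no other anchor, so N(protocol rule) = N(SAP) + G, with G ≥ 0. In 200,000 arbitrary generated sequences the SAP count never exceeded the count with the rule added.

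**Step 4: size.** G is not given. Assume a share f of SAP-counted treated bleeds hides one extra bleed. Then the ABR with the rule = ABR(SAP) × (1 + f), and the relative shortfall is f/(1 + f).

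- f = 2%: 0.02/1.02 = 2.0%.
- f = 10%: 0.10/1.10 = 9.1%.
- f = 0: none.

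For illustration, take a SAP-based ABR of 2.9, the treated-bleed figure for emicizumab in the earlier randomised study (Protocol 1.2.2.3). With f = 10% it becomes 2.9 × 1.10 = 3.19. One extra bleed in one patient followed for 2 years adds 365.25/730.5 = 0.5 to that patient's calculated ABR.

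**Step 5: per-bleed summaries.** For RE–2h–T–100h–T the SAP reports one bleed with the dose of both injections and a duration of 100 h (100/24, about 4.2 days). The protocol gives two bleeds with one injection each.

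**Step 6: another difference, pulling the other way.** The clause in SAP 2.2.2.3 about a different location cuts the window short. In RE–2h–T–10h–LE–2h–T–70h–RE–2h–T the last RE is 10 + 2 + 70 = 82 h after the only treatment tied to the first RE, so the SAP counts 3. If the second T also treated the right elbow, the protocol gap is 70 h and the count is 2.

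**The case against.** The strongest reply is that the two documents differ only when an injection follows the last by more than 72 hours and no new bleed is recorded. Patients record bleeds and medication at least weekly, and investigators review the records for completeness, so this may be rare or absent. That stands, and it rules out three stronger readings. A reader might infer that the treated ABR is in fact lowered; the documents give no frequency, so the effect may be nil. A reader might infer that prolonged or recurrent treatment in general is collapsed into one bleed; treatment with gaps up to 72 hours, and recurrences that are recorded, are counted alike under both documents. A reader might infer that the SAP as a whole departs from the protocol in the drug's favour; Step 6 shows a clause that can raise the count.

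It can also be said that the SAP history would not list a rule that was never in the SAP. That is fair: the history logs changes between versions, so its silence proves little. The point rests on the text of the two definitions.

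The phrase in 4.6.1.6 and 4.9.1.2 about linking by the 72h rule might be read as a gap limit. But 2.2.2.3 sets none between injections, and even on that reading a detached injection would not become a bleed.

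Finally, efficacy is a secondary objective, the analyses are descriptive, and the listing in 2.2.2.3 keeps the raw data visible. These limit the consequences but do not remove the conflict: the estimated rate is itself the efficacy result, and the listing flags merged bleed records, not long injection gaps.

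**Conclusion.** The concern holds in a limited form. The SAP leaves out the protocol's splitting rule, and following it as written gives a treated-bleed count that conflicts with Protocol 4.5.7.1 whenever an injection gap above 72 hours has no new bleed record. That is a wrong result in those cases, not just missing detail. Considered alone, the omission works in one direction: it lowers the count or leaves it unchanged. The shortfall of about 2.0% to 9.1% in the treated ABR rests entirely on the assumed share of 2% to 10% with one hidden bleed each; the documents supply no figure, and zero is possible. Pooling in the per-bleed dose and duration summaries depends on the same unknown frequency. No claim is made about the net effect of all the differences between the SAP and protocol definitions.

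**What to change.** Add to SAP 2.2.2.3 that a treatment for bleed given more than 72 hours after the preceding treatment, with no bleed recorded in between, starts a new bleed that inherits the location, type, cause and symptoms of the bleed it follows. The inheritance has to be written down. SAP 4.11 counts a missing cause as spontaneous, which would inflate treated spontaneous bleeds, and SAP 2.2.2.7 requires a reported symptom for a treated joint bleed. The text should also say how the new bleed is assigned when the earlier treatment was shared by same-day bleeds at two sites.

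If the main analysis is meant to stay aligned with the sister studies, keep the present rule, state openly that it departs from Protocol 4.5.7.1, and add the splitting rule as a sensitivity analysis in SAP 4.6.6. Either way, report the number of injection gaps above 72 hours without a new bleed record, since that settles whether the point matters.

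The cost is a few lines of derivation on treatment times already collected, and possibly a slightly higher ABR.

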### **2.2.2.7 Treated Joint Bleeds**

Joint bleeds are defined as bleeds where the bleed type is “joint” and at least one of the following symptoms has been observed: increased swelling or warmth of the skin over the joint, increased pain in the joint or decreased range of motion, or difficulty moving the joint compared to baseline.

For the analysis, all treated bleeds that fulfill the above joint bleeds definition will be included and then the 72-hour rule will be applied. Bleeds due to procedure/surgery will be excluded.

In case multiple bleeds are counted as one bleed (72h rule), all of these bleeds needs to fulfill the above rule.

Additional analyses will be performed for joint bleeds where the bleed site is “joint”, regardless of any accompanying reported symptom.

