#### **4.6.1.1 Bleeds**

The primary analysis will be based on treated bleeds (see definition 2.2.2.2). The number of bleeds over time will be estimated using a negative binomial (NB) regression model, which accounts for different follow-up times. The time that each patient stays in the study (efficacy period) will be included as an offset in the model.

An additional model which adjusts for number of bleeds (< 9 or ≥ 9, according to eCRF) in the last 24 weeks prior to study entry will be used to support the primary analysis.

In the rare case that the negative binomial model does not converge or no bleeds were observed for a given endpoint, the primary analysis will be based on “calculated” annualized bleed rate (ABR).

The ABR is calculated using the following formula (called Calculated ABR on all outputs):

$$\frac{\text{Number of bleeds during the efficacy period}}{\text{Number of days during efficacy period}} \times 365.25$$

The efficacy analyses will include the following endpoints defined in section 2.2.2: treated bleeds, all bleeds, treated joint bleeds, treated target joint bleeds and treated spontaneous bleeds. For each endpoint, the model based ABR will be estimated along with its corresponding 95% CI. In addition, the mean, 95% CI based on Exact Poisson, median, IQR, min and max will be provided for the calculated ABR.

A corresponding listing will be provided which will include for each patient the duration of efficacy period, number of bleeds together with calculated ABR for treated bleeds, all bleeds, treated spontaneous bleeds, treated joint bleeds and treated target joint bleeds (based on data before up-titration only). A separate listing will also be provided for the up-titrated population, based on data on or after the up-titration.

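### For other/other bleeds the 72-hour rule sets aside the recorded site, so two bleeds at different sites can be counted as one, and the count can only move down

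*SAP*

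**What the plan says.** SAP 2.2.2.3 sets three conditions for merging. Two bleeds must be of the same type "and the same etiology and at the same anatomical location are considered to be one bleed if the second occurs within 72 hours" of the last treatment for the first. SAP 2.2.2.4 starts the 72 hours at the bleed itself when it was not treated. Two further rules limit or extend merging:

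- "Any bleed with a different etiology is considered a separate bleed regardless of time from last injection".
- "In case of trauma with multiple different locations of bleed, this will be considered as one bleed for the analyses".

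The exception at issue stands in the same section: where the location is other/other, "other/other is used as the bleed location and not the exact location entered on the separate eCRF page". No reason is given.

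Protocol 4.5.7.1 has no such exception. It treats as one bleed those "which have any symptoms of bleeding at the same location or injections are" no more than 72 hours apart.

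The rule feeds the main efficacy result, since SAP 4.6.1.1 states: "The primary analysis will be based on treated bleeds". It also feeds all bleeds (2.2.2.4) and treated spontaneous bleeds (2.2.2.9).

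**The concern.** The location test exists so that a continuing bleed is counted once and a new bleed elsewhere is counted separately. The worked examples in SAP 2.2.2.4 apply it strictly: right and left elbow are different locations, so side alone separates two bleeds. For other/other the same section replaces the site by a residual label, although the site has been collected. Two unrelated sites then pass as the same location.

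Three things follow.

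- **Direction.** The label is a coarser grouping than the site. Any pair that merges on the site also merges on the label, so the count under the label can equal or fall below the count under the site, never exceed it. Fewer bleeds favour the drug.
- **Per-bleed exposure.** SAP 4.6.1.6 and 4.9.1.2 attach to one bleed all treatments linked by the 72-hour rule. A cross-site merge adds two courses together, so infusions, dose per kg and duration per bleed rise, and a bleed can move up a dose band. Annualized infusions and doses in 4.6.1.6 are divided by time, not bleeds, and do not change.
- **Etiology check.** SAP 4.11 counts bleeds with missing cause as spontaneous. Two bleeds of unknown cause would then share an etiology.

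**Working it through.** **1. The plan's own examples.** Apply the rule as written: a bleed joins the preceding bleed at the same location if it starts within 72 hours of the last linked treatment, or of that bleed if untreated. The six sequences in SAP 2.2.2.4 give 2, 2, 1, 1, 2 and 3 bleeds, as the SAP states. In the fourth, bleeds 50 h and then 30 h apart count as one, although the third is 50 + 30 = 80 h after the first. Merging can therefore chain.

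**2. The same rule on an other/other pair.** Take a bleed at site A treated 2 h later, and a bleed of the same etiology at site B some hours after that treatment.

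| Gap from treatment to second bleed | Count using the label | Count using the exact site |
|---|---|---|
| 48 h | 1 | 2 |
| 75 h | 2 | 2 |

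**3. Where it cannot act.** Bleeds of different etiology stay separate. Multi-site trauma is one bleed under both documents. In SAP 2.2.2.7, "Joint bleeds are defined as bleeds where the bleed type is" joint, so bleeds of type other lie outside the joint endpoint and the target joint endpoint built on it.

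**4. Size, on assumptions.** The documents give neither the other/other share nor the frequency of close pairs. For scale only, take the emicizumab arm of the earlier Phase III study in inhibitor patients (protocol 1.2.2.3): treated ABR 2.9 with 62.9% of patients bleed-free, and all-bleeds ABR 5.5 with 37.1% bleed-free. Assume 24 weeks of observation.

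- Mean count m = ABR × 24/52: 1.338 treated, 2.538 all.
- Negative binomial dispersion k from (1 + k·m)^(−1/k) = bleed-free share: k = 3.98 treated, 1.67 all.
- Share of bleeds lost = s² × ABR × (1 + k) × w/365.25, where s is the other/other share and w the window in days (3, or 5 if treatment lengthens it).

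For example, treated bleeds with s = 0.40 and w = 5: 0.16 × 2.9 × 4.98 × 5/365.25 = 3.16%.

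| s | w (days) | Treated ABR lost | All-bleeds ABR lost |
|---|---|---|---|
| 5% | 3 | 0.03% | 0.03% |
| 5% | 5 | 0.05% | 0.05% |
| 10% | 3 | 0.12% | 0.12% |
| 10% | 5 | 0.20% | 0.20% |
| 20% | 3 | 0.47% | 0.48% |
| 20% | 5 | 0.79% | 0.80% |
| 40% | 3 | 1.90% | 1.93% |
| 40% | 5 | 3.16% | 3.22% |

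The treated ABR of 2.90 would become 2.899 to 2.808, and the all-bleeds ABR of 5.50 would become 5.498 to 5.323. The formula is generous in treating every close pair as same etiology and different site. It is not generous in assuming no clustering in time within a patient and the same s for everyone. With clustering, write the loss as s × c, where c is the fraction of other/other bleeds wrongly merged: 0.20 × 0.10 = 2.0%, and 0.40 × 0.25 = 10%.

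**The case against.** **The SAP already has safeguards.** SAP 4.6.6 plans an analysis without the 72-hour rule for every bleed endpoint, 4.6.1.3 summarises all bleeds by location without it, and the listing in 2.2.2.3 flags bleeds not counted separately. This stands in part. The count without the rule is at least the exact-site count, which is at least the label count, so the analysis is a valid upper bound. But it drops the whole rule and, as worded, the restriction to treated bleeds as well, so it cannot show what the label alone does. The listing is described as showing the Bleed Record, while the exact site is on a separate page, so a reader may not see which merges crossed sites.

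**The protocol is not flatly contradicted.** A reader might infer that the protocol merges only at the same site. Its wording joins same location and injections close in time with an "or"-type alternative, and the second limb could be read as merging on timing alone. This stands. The firm inconsistency is within the SAP: between its own location condition and examples, and the label exception.

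**Stronger readings do not hold.** A reader might infer that bleeds at different sites are generally merged and the rate is understated as a fact. Merging needs both bleeds to be other/other, of the same etiology and inside the window. Nor do the documents show which sites fall under other/other, since the location list is not given; nose or gastrointestinal bleeds may have their own codes. Nor is the chance of a second bleed within 3 days, for example 1 − exp(−2.9 × 3/365.25) = 2.3%, the bias in the ABR: it treats every bleed as other/other.

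**Consequence and cost.** Bleeds are a secondary, descriptive endpoint, and no sample size or decision rule rests on them. Using sites verbatim could also split one bleed recorded under two names. Both points stand; the second shapes the fix.

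**Conclusion.** The point holds in limited form. For other/other bleeds the SAP abandons its own location condition without giving a reason, and it can count two bleeds at different sites as one. The effect on treated, all and treated spontaneous bleed counts can only be downward, and on infusions and dose per bleed upward.

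The size is unknown because the other/other share is unknown. Under the assumptions shown it is below 1% of the ABR if other/other makes up 20% of bleeds or fewer, and about 3.2% at a 40% share with a 5-day window. Strong clustering could take it to several percent, or 10% in the extreme case shown. The documents do not support a claim that the reported rate is materially biased. They do support using information that is already collected.

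**What to change.** Replace the exception in SAP 2.2.2.3 along these lines: for other/other bleeds the 72-hour rule is applied to the exact site entered on the eCRF page, coded to site groups fixed before the analysis, with side where the site has one; if the exact site is missing, other/other is used as the location.

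Fixing the groups in advance prevents synonyms for one site from being split. Side should not be required for midline sites.

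Two additions to reporting:

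- Show the exact site in the bleed listing.
- Report how many other/other bleeds would be merged across different sites under the label.

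If the label is kept as the main rule, for instance for consistency with other studies, run the exact-site version as a sensitivity analysis for treated, all and treated spontaneous bleeds, and for the per-bleed exposure tables.

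The cost is a short SAP edit, minor coding of sites, and an ABR that may come out slightly higher.
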